4.2 Number of Patients

Thirty subjects will be enrolled on Part 1 and, therefore, up to a maximum of 30 subjects will receive OncoTreat-prioritized agents on Part 2. No subjects will be replaced.

4.3 Study Drugs

4.3.1 Capecitabine

The cycle length will be 21 days, and 1000 mg/m^2 given orally twice per day, usually separated 12 hours apart, on Days 1-14 of a 21-day cycle. Capecitabine should be taken with water within 30 minutes after a meal.

4.3.2 Imatinib

The cycle length will be 28 days. Patients will receive imatinib 400 mg orally once daily. A dose increase up to 800 mg daily (given as 400 mg twice daily) may be considered by the investigator, as clinically indicated, in patients showing clear signs or symptoms of disease progression at a lower dose and in the absence of severe adverse drug reactions.

4.3.3 Ruxolitinib

The cycle length will be 28 days. Patients will receive ruxolitinib 15 mg orally twice per day. A dose increase up to a maximum of 25 mg twice daily may be considered by the investigator, as clinically indicated, in patients showing clear signs or symptoms of disease progression at a lower dose and/or in the absence of severe adverse drug reactions.

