(7) Subjects who are initiated on an OncoTreat-prioritized drug will have an optional ontreatment 'pharmacodynamic' biopsy performed within one month of initiating treatment and within 24 hours of the most recent dose. This biopsy will be performed as 'proof-of-principle' that OncoTreat prioritized drugs result in collapse of the master regulator architecture (also known as master regulator signature) of the tumor, *in vivo*.

(8) Peripheral blood will be drawn for routine laboratory testing, tumor markers (CA 19-9), and research testing for biomarker analysis. Pharmacology measurements will also be drawn weekly during Cycle 1 of treatment. [name], the Director of Clinical Pharmacology and Toxicology Laboratory (CPTL), will make available CLIA assays for every FDA-approved drug and will provide assays for any investigational agents that match to the subjects in the study. Pharmacokinetic (PK) results and toxicity may be used by the treating physician, after discussion with the Investigator, to modify dosing schedule as appropriate.

(9) Adverse events will be monitored and recorded (Section 8).

(10) Subjects will undergo routine standard-of-care radiographic assessments (CT preferred) at baseline and every 8 weeks with response measured per RECIST v1.1 (Section 10).

(11) Subjects will continue on study treatment until radiographic disease progression or death, intolerance to the study drug, or withdrawal of consent. Patients will not be permitted to continue study treatment after disease progression per RECIST v1.1 criteria (Section 10).

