Ruxolitinib inhibits the Janus-associated kinase-1 and -2 (JAK 1/2) enzymes and is FDAapproved for the treatment of myelofibrosis, polycythemia vera, and graft-versus-host disease. CYP3A4 is the major enzyme mediating hydroxylation of ruxolitinib. Different formulations are available for this drug from 5 mg to 20 mg tablets. Ruxolitinib has a $t_{1/2}$ of 2.6 - 5 hours, a t_{max} of 1 - 3 hours, and reaches a C_{max} of 60 or 570 ng/mL for doses of 5 mg or 50 mg, respectively [76, 77].

Dosage: Ruxolitinib 15 mg BID given orally twice per day. A dose increase up to 25 mg BID may be considered by the investigator, as clinically indicated, in patients showing clear signs or symptoms of disease progression at a lower dose and in the absence of severe adverse drug reactions.

Sampling: Trough levels of ruxolitinib will be measured on day 2 at 24 ± 3 hours post-dose. On day 2, the trough level is expected at a concentration around 3 ng/mL [77].

Sample Handing: Peripheral blood will be collected in a tube and will be allowed to clot for 30 - 60 min following by centrifugation at 3000 rpm, 4°C, for 10 min.

Extraction: Ruxolitinib will be extracted from the serum samples using the above mentioned protein precipitation extraction procedure. Minimum volume of blood sample considering duplicates for TDM (and PK) studies should be no less than 300 μ L (120 μ L is needed for one extraction).

Quantification: Concentration of ruxolitinib will be measured by a New York State Department of Health (and thereby CLIA-) approved LC-MS/MS assay developed for the simultaneous quantification of OncoTreat-prioritized drugs. The method is based on an existing New York State DOH-approved assay for imatinib developed by CPTL for its clinical services, with only minor modifications.

Target Range: The target range for ruxolitinib trough concentration in serum will be 15 - 60 ng/mL.

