4.9.4.2 Dose Modification Based on Response

If efficacy is considered insufficient and platelet and neutrophil counts are adequate, doses may be increased in 5 mg twice daily increments to a maximum of 25 mg twice daily. Doses should not be increased during the first 4 weeks of therapy and not more frequently than every 2 weeks.

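### The ruxolitinib dose-increase rule appears in three forms that do not agree, and increases triggered by signs of progression conflict with the unqualified stop at progression in the synopsis and Section 7.2

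*Combined protocol and SAP*

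**What the plan says.** Three sections govern a ruxolitinib dose increase.

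- **Section 4.3.3** leaves an increase, with a ceiling of 25 mg twice daily, to the investigator's clinical judgement. Its condition reads: "in patients showing clear signs or symptoms of disease progression at a lower dose and/or in the absence of severe adverse drug reactions".
- **Section 4.8.3** sets the same ceiling and gives the same discretion. Its condition reads: "in patients showing clear signs or symptoms of disease progression at a lower dose and in the absence of severe adverse drug reactions".
- **Section 4.9.4.2:** "If efficacy is considered insufficient and platelet and neutrophil counts are adequate, doses may be increased in 5 mg twice daily increments", to the same ceiling of 25 mg twice daily. It adds: "Doses should not be increased during the first 4 weeks of therapy and not more frequently than every 2 weeks".

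The imatinib increase from 400 to 800 mg daily (Sections 4.3.2 and 4.8.2) uses *and* in both places and also takes signs or symptoms of progression as its trigger.

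Four places govern stopping at progression.

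- **Section 4.1(11)** names radiographic progression and adds: "Patients will not be permitted to continue study treatment after disease progression per RECIST v1.1 criteria".
- **Section 5.5** requires discontinuation for radiographic progression if confirmed by RECIST v1.1.
- **Section 7.2 and the synopsis row on duration of administration** end treatment at progression, with no radiographic or RECIST qualifier.

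**The concern.** An investigator who consults one section will apply different conditions from one who consults another. The conditions in dispute are the ones that limit risk: whether a severe adverse reaction rules out an increase, whether blood counts must be adequate, how large a step may be, and how early it may come. The ceiling matters too. Section 4.6.3 reports that 25 mg twice daily was one of the two schedules established as the maximum tolerated dose in the cited myelofibrosis study, because of thrombocytopenia.

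The second problem concerns progression. A subject with signs of progression qualifies for a higher dose under the increase rules and for stopping under Section 7.2. The choice between them determines whether that subject is counted under dose modifications or under discontinuations, both part of a secondary endpoint in Section 2.2.2.

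**Working it through.** No planned figure depends on this, so the check is a comparison of the text plus some short arithmetic.

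**1. The three increase rules side by side**

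| Condition | 4.3.3 | 4.8.3 | 4.9.4.2 |
|---|---|---|---|
| Ceiling (twice daily) | 25 mg | 25 mg | 25 mg |
| Signs or symptoms of progression | sufficient alone, read literally | required | not mentioned; trigger is insufficient efficacy |
| No severe adverse drug reaction | sufficient alone, read literally | required | not mentioned |
| Adequate platelets and neutrophils | not mentioned | not mentioned | required |
| Step size | none given | none given | 5 mg twice daily |
| Timing | none given | none given | none in first 4 weeks, then no more often than every 2 weeks |
| Reference to the other two | none | none | none |

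**2. Where *and/or* and *and* part.** Let P be signs of progression and S a severe adverse reaction.

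- P present, S absent: both sections allow an increase.
- P present, S present: 4.3.3 allows it, 4.8.3 does not.
- P absent, S absent: 4.3.3 allows it, 4.8.3 does not.
- P absent, S present: neither allows it.

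The two sections disagree in 2 of the 4 cases.

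**3. Step size and timing.** From 15 to 25 mg twice daily, Section 4.9.4.2 needs (25 − 15)/5 = 2 steps. The first cannot fall in the first 4 weeks and the second must be at least 2 weeks later, so the ceiling is reached no earlier than 4 + 2 = 6 weeks. Sections 4.3.3 and 4.8.3, read alone, set no earliest date and allow a single 10 mg step.

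**4. Size of the increase.** Ruxolitinib: 25/15 = 1.67, or +67% at the ceiling. Imatinib: 800/400 = 2. These are maximum dose ratios.

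**5. Increase on progression against stopping at progression**

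- *Against 4.1(11) and 5.5:* stopping is tied to radiographic or RECIST progression. Signs or symptoms can precede that, and on-study scans are 8 weeks apart (Section 9.1, note h). An increase before RECIST progression is compatible with these sections.
- *Against 7.2 and the synopsis:* progression is unqualified. A subject judged to show clear signs of progression can meet the stopping criterion and the increase trigger together. No section says which governs.
- *Section 4.9.4.2* does not mention progression and is not part of this conflict.

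**6. Effect on the descriptive counts.** The plan's minimum number treated is 0.30 × 30 = 9 (Section 12); the synopsis estimates that 15 subjects will progress to Part 2. One subject handled differently moves an incidence by 1/9 = 11.1 percentage points, or by 1/15 = 6.7. The number who will receive ruxolitinib or imatinib is not given.

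**The case against.** The strongest reply is that this is one loose connective surrounded by other safeguards. An increase may only be considered, and only as clinically indicated. Unacceptable toxicity requires discontinuation (Section 5.5). Section 4.9.4.1 sets platelet-based reductions and holds, and 4.9.4.2 can be read as adding detail to the other two sections, since it shares their ceiling. This softens the likely harm and it stands to that extent. It does not settle which conditions bind: discretion is exercised within a rule, and here the rule differs by section. Reading all three together still leaves *and/or* against *and*, and insufficient efficacy against signs of progression.

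A second reply is that the protocol distinguishes clinical from radiographic progression. Sections 4.1(11) and 5.5 do so, and Section 10.5.3 separates symptomatic deterioration from objective progression. This stands for those sections. It does not answer Section 7.2 or the synopsis.

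Some stronger readings are tempting but unsupported:

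- *That every version escalates on progression.* Section 4.9.4.2 does not.
- *That escalation contradicts every stopping rule.* It conflicts directly only with the two unqualified ones.
- *That PFS is biased.* Sections 2.2.2 and 10.7.2 define PFS by RECIST progression or death, and note h of Section 9.1 keeps scans on calendar time despite dose interruptions. A subject who is alive without RECIST progression has had no event at any dose.
- *That all ruxolitinib subjects are affected.* Only those considered for a discretionary increase are.

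**Conclusion.** The inconsistency is real and verbatim. For the same drug and ceiling, Section 4.3.3 read literally permits increases that 4.8.3 bars and increases that 4.9.4.2 bars. The progression conflict is narrower: the ruxolitinib and imatinib increases in Sections 4.3.2, 4.3.3, 4.8.2 and 4.8.3 conflict with the synopsis and Section 7.2, and are in tension, but not strict contradiction, with Sections 4.1(11) and 5.5.

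The consequence is a safety ambiguity over an increase of up to 67% for ruxolitinib, and inconsistent counts of dose modifications and discontinuations. Those counts are descriptive, with no test or threshold attached, and Section 2.2.2 says safety endpoints will not be assessed by drug, so no primary conclusion depends on them. The verdict rests on a literal reading of *and/or* and on the absence of any cross-reference or order of precedence among the three sections. That imatinib consistently uses *and* shows that the two drugs are worded differently; it does not establish what was intended for ruxolitinib.

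**What to change.** - Reconcile Sections 4.3.3, 4.8.3 and 4.9.4.2 into one ruxolitinib dose-increase rule. State it once, covering trigger, adverse-reaction condition, blood counts, step size and timing, and have the other two sections refer to it.
- Reconcile the progression wording in the synopsis and Section 7.2 with Sections 4.1(11) and 5.5. Then say how signs or symptoms of progression that may prompt a ruxolitinib or imatinib increase relate to progression that ends treatment.

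Which clinical conditions apply is for the sponsor to decide. The cost is a wording amendment; no sample size, visit or analysis changes.

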4.4 Tumor Biopsies

A tissue sample, from either the primary or metastatic site, will be obtained from all treatmentnaïve subjects at the time of initial presentation. This biopsy, therefore, will serve both diagnostic and research purposes prior to initiation of first-line chemotherapy. Tumor tissue acquision, handling, and processing are described in the laboratory manual.

Subjects for whom an OncoTreat-prioritized agent is identified will undergo a repeat biopsy prior to starting the study drug. This will confirm no change in master regulator profile, which is not expected, and that the OncoTreat-prioritized agent identified from the pre-treatment sample is no different than the agent identified now following treatment with chemotherapy.

The window for each biopsy is outlined in the study calendar (Section 9).

4.5 Pharmacology: Pharmacodynamics and Pharmacokinetics 4.5.1 **Capecitabine**

Capecitabine (N-[1-(5-deoxy-β-D-ribofuranosyl)-5-fluoro-1,2-dihydro-2-oxo-4-pyridinyl]*n*-pentyl carbamate) is a crystalline substance with a molecular weight of 359.35. It is highly soluble in water and stable in tablet form for at least 9 months [42]. Capecitabine is metabolized to the only active compound, FU, via 3 metabolic steps. Once capecitabine is absorbed through the intestine, liver carboxylesterase converts it to 5'-deoxy-5fluorocytidine (5'-DFCR). 5'DFCR is then metabolized to 5'DFUR by cytidine deaminase, a ubiquitous enzyme with high concentrations in the liver, plasma, and tumor tissue. Finally, 5'DFUR is converted to the active drug FU by thymidine phosphorylase, found in amounts 3 to 10 times higher in various solid tumors compared with normal adjacent tissue [42-44]. The localization of this enzyme to the liver and tumor tissue allows for targeted intratumor release of FU.

Relative FU concentrations in colorectal tumor tissue, adjacent healthy tissue, and plasma were compared in 19 patients undergoing surgical resection of their primary and/or liver metastasis [44]. Capecitabine 1255 mg/m² twice daily given orally within 30 minutes of food was administered 5 to 7 days before surgery. Samples of the aforementioned tissue from each patients were evaluated for concentrations of capecitabine and its metabolites as well as enzymes involved in its metabolism. Activity of thymidine phosphorylase was almost 4 times higher in colorectal tumor compared with healthy tissue. Consequently, concentrations of FU were 3.2 times higher in primary colorectal tumors compared with surrounding healthy tissue (P = 0.002). The tumor tissue: plasma ratio for the active drug was 21.4 and normal tissue:plasma ratio was 8.89. This selectivity was not demonstrated between liver metastasis and healthy liver tissue, however, with a thymidine phosphorylase activity ratio close to 1 and FU concentration ratio of 1.41 (P = 0.49) [44].

Capecitabine has almost 100% oral bioavailability and exhibits linear increases in C_{max} and AUC with dosage increases [45]. After 2 doses of 1250 mg/m², the drug undergoes rapid absorption, with peak plasma levels of 3.9 mg/L achieved in 1.5 to 2 hours. In comparison, C_{max} for the active metabolite FU was lower at 0.66 mg/L with a similar T_{max} of 2 hours. AUC values for the parent drug and active metabolite for the same dosage were 5.96 mg and 1.34 mg h/L, respectively. In a study of 34 patients undergoing 14 continuous days of capecitabine therapy at daily doses ranging from 502 to 3514 mg/m², no significant accumulation of capecitabine or its metabolites was seen [45, 46].

A crossover study evaluated the effect of food on capecitabine pharmacokinetics in 11 patients with colorectal cancer [47]. Doses of 666 or 1255 mg/m² give twice daily were administered either after an overnight fast or within 30 minutes of finishing a standard breakfast on days 1 and 8. The AUC of capecitabine decreased in the presence of food but the AUC of the cytotoxic drug FU was only minimally affected. Dosing with food is still recommended, as this was how the drug was dosed in clinical trials and because the reported response rate and toxicity profiles reflect the administration of capecitabine within 30 minutes of finishing a meal.

The predominant route of elimination is renal. The use of capecitabine in patients with renal impairment was compared in 24 patients with various solid tumors [48]. Capecitabine was dosed orally at 1250 mg/m2 twice daily for 2 weeks followed by a 1-week rest period. All 4 patients with severe renal dysfunction (defined as CrCl <30 mL/min) experienced serious grade 3 or 4 adverse effects. From these results, it is recommended that patients with CrCl 30 to 50 mL/min receive 75% of the recommended starting dose of capecitabine and that use of this agent be avoided in patients with CrCl <30 mL/min because of the potentially increased risk of adverse events.

No dosing adjustments for patients with hepatic dysfunction are recommended with capecitabine.

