consideration. If an OncoTreat-informed drug is identified and treatment is recommended by the PMTB, the subject may proceed with consent for Part 2.

The PMTB will convene at CUMC on a monthly or as needed basis. A quorum of at least 5 members, including the principal investigator, one additional medical oncologist and one non-Columbia individual, must be present for each meeting. Teleconference is permitted if a PMTB member is located off campus.

(5) If the PMTB recommends a FDA-approved or investigational oncology drug, and the drug is available, the subject will consent to Part 2 and begin the study agent at the time of disease progression or intolerance to therapy. A pre-study treatment biopsy will be required to confirm that the MR dependencies of the subject's tumor have not changed over time or in response to first-line therapy (a theoretical concept that needs to be formally assessed).

If no FDA-approved or investigational agents are identified at the time of first disease progression or intolerance to first-line therapy, or the OncoTreat-prioritized drug is not available in a time manner for administration, the subject will continue on to physician's choice second-line treatment (chemotherapy or clinical trial). The subject will be followed for response evaluation. At the time of second disease progression or intolerance to treatment, the subject will be re-evaluated for enrollment on Part 2. If a FDA-approved or investigational agent is identified, and the drug is available, the subject may consent to Part 2 and begin the study agent following a pre-study treatment biopsy. If no FDA-approved or investigational agents are identified, or the OncoTreat-prioritized drug is not available, the subject will screen fail for Part 2 and will be followed for response evaluation.

(6) The dosing and schedule of the OncoTreat-prioritized drug will be described in the subprotocol for each agent. For each of the FDA-approved drugs, the dose and dosing schedule will be aligned with the currently approved dose and schedule in the product U.S. Package Insert (USPI) and Investigator's Brochures (IBs). For the investigational agents, the dose and dosing schedule will be aligned with the current recommend phase 2 dose (R2PD).

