4.8.1 Capecitabine

Capecitabine is the oncology pro-drug of 5-fluorouracil (5FU). Capecitabine is administered orally and undergoes mainly hepatic metabolism where it is first biotransformed into 5'-deoxy-5-fluorocytidine (5'-DFCR) by carboxylesterases and subsequently to 5'-deoxy-5-fluorouridine (5'-DFUR) by cytidine deaminase. Metabolism of capecitabine involves different enxymes, where thymidine phosphorylase converts 5'-DFUR to the active drug 5FU [71].

Concentration levels of capecitabine and both 5'-DFCR and 5'-DFUR are measured in PK studies [72]. Several PK studies were assessed previously in serum for capecitabine, where t_{max} ranged from 0.5 to 2 hours, with a C_{max} of 5000-9500 ng/mL and $t_{1/2}$ of 34-50 min. After the administration of a standard dose of capecitabine, it might be expected serum concentrations within 5-10,000 ng/mL.

Dosage: Capecitabine 1000 mg/m² given orally twice daily, separated 12 hours apart, on Days 1-14 of a 21-day cycle, to be taken with water within 30 minutes after a meal.

Sampling: Based on a 21-day cycle, as mentioned above, peak levels will be measured 2 hours after administration of capecitabine on day 1 and cycle 1 day 8.

Sample Handling: Peripheral blood will be collected in a tube containing 500 nM tetrahydrouridine (THU) to avoid *ex vivo* conversion of 5'-DFCR to 5'-DFUR [73] and will be allowed to clot for 30-60 min followed by centrifugation at 3000 rpm, 4°C, for 10 min.

Sample Storage: Serum samples will be stored at -80°C.

Extraction: Capecitabine will be extracted from the serum samples using the above mentioned protein precipitation extraction procedure. Minimum volume of blood sample considering duplicates for TDM (and PK) studies should be no less than 300 μ L (120 μ L is needed for one extraction).

Quantification: Concentration of capecitabine will be measured by a New York State Department of Health (and thereby CLIA-) approved LC-MS/MS assay developed for the

simultaneous quantification of OncoTreat-prioritized drugs. The method is based on an existing New York State DOH-approved assay for imatinib developed by CPTL for its clinical services, with only minor modifications.

Target Range: The target ranges for peak levels will be 5,000 - 10,000 ng/mL for capecitabine in serum.

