4.9.4.3 Dose Adjustment with Concomitant Strong CYP3A4 Inhibitors

On the basis of pharmacokinetic studies in healthy volunteers, when administering ruxolitinib with strong CYP3A4 inhibitors (such as but not limited to boceprevir, clarithromycin, conivaptan, grapefruit juice, indinavir, itraconazole, ketoconazole, lopinavir/ritonavir, mibefradil, nefazodone, nelfinavir, posaconazole, ritonavir, saquinavir, telaprevir, telithromycin, voriconazole), the recommended starting dose is 10 mg twice daily for patients with a platelet count greater than or equal to 100,000. Additional dose modifications should be made with careful monitoring of safety and efficacy.

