5.1 Inclusion Criteria

In order to be eligible for participation in this trial, the subject must:

- Be willing and able to provide written informed consent for the trial.
- Age ≥ 18 years of age on day of signing informed consent.
- Have histologically or cytologically confirmed diagnosis of pancreatic ductal adenocarcinoma.
- Have a predicted life expectancy of greater than 3 months.
- Have measurable disease based on RECIST v1.1.
- Have a performance status of 0 or 1 using the ECOG Performance Scale
- Have documented radiographic or clinical progression to or documented intolerance to 5-FU- or gemcitabine-based systemic therapy for locally advanced, unresectable or metastastic disease. Patients for whom targeted therapy.
- MSI-H/dMMR or NTRK-fusion positive tumors
 - Subjects must have received prior treatment with approved drugs for tumors harboring these aberrations.
- Have a negative urine or serum pregnancy test within 72 hours prior to receiving the first dose of study medication (female subjects of childbearing potential). If the urine test is positive or cannot be confirmed as negative, a serum pregnancy test will be required.
- Be willing to use an adequate method of contraception for the course of the study through 120 days after the last dose of study medication (male and female subjects of childbearing potential).
- Demonstrate adequate organ function as defined below in Table 5.

Table 5Adequate Organ Function Laboratory Values

	0	e e
System		Laboratory Value

Hematological	
Leukocytes	≥2,000 /mcL
Absolute neutrophil count (ANC)	≥1,500 /mcL
Platelets	≥100,000 /mcL
Hemoglobin	≥9 g/dL without transfusion or EPO
	dependency within 7 days
Renal	
Creatinine OR	\leq 1.5 X upper limit of normal (ULN) OR
Measured or calculated ^a creatinine	\geq 60 mL/min for subject with creatinine levels
clearance (GFR can also be used in	>1.5 X institutional ULN
place of creatinine or CrCl)	
Hepatic	
Total bilirubin	$\leq 2 \text{ mg/dL}$ or direct bilirubin $\leq \text{ULN}$ for those
	with total bilirubin >2 X ULN
	Subjects with Gilbert Syndrome will be
AST (SCOT) and ALT (SCDT)	eligible if total bilirubin is $<3.0 \text{ mg/dL}$
ASI (SGOI) and ALI (SGPI)	<2.5 X ULN OR <5 X ULN for subjects with liver metastases
Albumin	>3.0 mg/dL
Coagulation	
Coagulation	
INR or PT	≤1.5 X ULN unless subject is receiving
aPTT	anticoagulant therapy as long as PT or aPTT
	is within therapeutic range of intended use of
	anticoagulants

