5.2 Exclusion Criteria

The subject must be excluded from participating in the trial if the subject:

- Is currently participating and receiving study therapy or has participated in a study of an investigational agent and received study therapy, or herbal/complementary oral or IV medicine, within 2 weeks of the first dose of treatment.
- All toxicities attributed to prior anti-cancer therapy other than alopecia and fatigue must have resolved to Grade 1 (NCI CTCAE v4.0) or baseline prior to administration of first dose of study drug. Subjects with toxicities attributed to prior anti-cancer therapy that are not expected to resolve and result in long-lasting sequalae, such as chronic neuropathy after platinum-based therapy, are permitted to enroll.

- Has received chemotherapy or radiotherapy within 14 days of first dose of study medication.
- Has a solid organ or hematologic transplant.
- Has experienced weight loss >10% over 2 months prior to first dose of study therapy.
- Has a diagnosed additional malignancy within 2 years prior to first dose of trial treatment with the exception of curatively treated basal cell carcinoma of the skin, squamous cell carcinoma of the skin or curatively resected in situ breast cancers. Subjects with another malignancy diagnosed >2 years prior to the first dose of trial medication who were treated with curative intent and are not undergoing active therapy will be eligible.
- Has an active infection requiring systemic therapy.
- Has clinically relevant ascites (defined as requiring paracentesis within 21 days of first dose of study drug) or with moderate radiographic ascites. A minimal amount of radiographic ascites is allowed.
- Has a history or current evidence of any condition, therapy, or laboratory abnormality that might confound the results of the trial, interfere with the subject's participation for the full duration of the trial, or is not in the best interest of the subject to participate, in the opinion of the investigator, including dialysis.
- Has a known psychiatric or substance abuse disorders that would interfere with cooperation with the requirements of the trial.
- Is pregnant or breastfeeding, or expecting to conceive or father children within the projected duration of the trial, starting with the screening visit through 120 days after the last dose of trial treatment.

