5.2.1 Exclusion Criteria Specific to Capecitabine

The subject must be excluded from receiving capecitabine if the subject:

- Requires concomitant use of phenytoin and/or warfarin due to reported increases in serum phenytoin levels and the international normalized ratio (INR) in patients receiving concomitant phenytoin and warfarin, respectively.
- Has a known hypersensitivity to capecitabine or to any of its components.
- Has a known hypersensitivity to 5-fluorouracil.

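### Section 4.5.1 reports advice to avoid capecitabine at CrCl below 30 mL/min, but no visible eligibility rule applies it: Table 5 accepts creatinine alone and 5.2.1 has no renal limit

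*Combined protocol and SAP*

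**What the plan says.** **Background.** Section 4.5.1 describes capecitabine as mainly renally eliminated. It summarises a 24-patient study at 1250 mg/m² twice daily in which all 4 patients with CrCl below 30 mL/min had serious grade 3 or 4 effects. It then passes on the recommendation that "use of this agent be avoided in patients with CrCl <30 mL/min because of the potentially increased risk of adverse events".

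**Eligibility.** The renal row of Table 5 (Section 5.1) offers two routes. Creatinine of at most 1.5 × ULN is enough by itself. The alternative is a clearance of at least 60 "mL/min for subject with creatinine levels" above that ceiling. Section 5.2.1 lists the exclusions particular to capecitabine. One reads "Requires concomitant use of phenytoin and/or warfarin due to reported increases in serum phenytoin levels" (and raised INR), and the others are hypersensitivity to capecitabine or to 5-fluorouracil. The nearest renal wording in the general exclusions (Section 5.2) ends a discretionary clause: "is not in the best interest of the subject to participate, in the opinion of the investigator, including dialysis".

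**Dose.** Section 4.3.1 sets 1000 mg/m² "given orally twice per day, usually separated 12 hours apart, on Days 1-14 of a 21-day cycle", and Section 4.8.1 repeats it. Neither makes the start depend on renal function. Table 2 (Section 4.9.2) changes the dose only by toxicity grade and number of appearances.

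**Text outside this document.** Section 4.1, step 6, states: "The dosing and schedule of the OncoTreat-prioritized drug will be described in the subprotocol for each agent". It also aligns the dosing of approved drugs with the package insert.

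**The concern.** Section 4.5.1 gives a numerical threshold and says to avoid the drug below it. That threshold does not reappear where subjects are screened or dosed. Serum creatinine alone is a poor guide to clearance in older or lighter people, and Section 5.1 sets no upper age limit. A subject admitted on creatinine may never have a clearance calculated.

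Elsewhere the protocol does turn drug-specific cautions into working rules. The phenytoin and warfarin exclusion is one. For ruxolitinib given with strong CYP3A4 inhibitors, Section 4.9.4.3 says "the recommended starting dose is 10 mg twice daily for patients with a platelet count greater than or equal to 100,000". That example concerns drug interaction, not renal function, so it shows only that the format is available.

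At stake is avoidable serious toxicity in an individual subject. No endpoint definition, sample size or power figure depends on it.

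**Working it through.** The plan gives no figure to reproduce. The check is a reading of the text, followed by an illustration of whether the gap can occur.

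**Step 1: where is a renal limit stated?**
- Section 4.5.1: avoid below 30 mL/min (background).
- Table 5, creatinine route: no clearance needed.
- Table 5, clearance route: at least 60 mL/min, asked only above 1.5 × ULN.
- Section 5.2.1: none.
- Section 5.2: dialysis only, within investigator opinion.
- Sections 4.3.1 and 4.8.1, and Table 2: none.
- Table 7 (capecitabine calendar): weight and a metabolic panel at screening, but no calculated clearance.

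So the visible rules apply the 30 mL/min threshold nowhere. The two routes in Table 5 are also uneven: just above the creatinine ceiling a subject must show at least 60 mL/min, and just below it nothing is asked.

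**Step 2: can a subject pass Table 5 with CrCl below 30?** The visible text names no formula and gives no ULN. Assumptions:
- Cockcroft-Gault: CrCl = (140 − age) × kg × (0.85 if female) ÷ (72 × creatinine in mg/dL).
- ULN 0.9 to 1.1 mg/dL for women, so the ceiling is 1.5 × ULN = 1.35 to 1.65.
- ULN 1.0 to 1.3 mg/dL for men, so the ceiling is 1.50 to 1.95.
- Ages and weights chosen for illustration.

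At the ceiling:
- Woman, 80 y, 50 kg: 60 × 50 × 0.85 ÷ 72 = 35.42. Then 35.42 ÷ 1.35 = 26.2 and 35.42 ÷ 1.65 = 21.5 mL/min.
- Woman, 75 y, 55 kg: 65 × 55 × 0.85 ÷ 72 = 42.20, giving 31.3 down to 25.6.
- Man, 80 y, 55 kg: 60 × 55 ÷ 72 = 45.83, giving 30.6 down to 23.5.
- Man, 65 y, 70 kg: 75 × 70 ÷ 72 = 72.92, giving 48.6 down to 37.4.

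The first subject is below 30 throughout the assumed ULN range. She crosses 30 at creatinine 35.42 ÷ 30 = 1.18 mg/dL, which is 1.31 × ULN (ULN 0.9) to 1.07 × ULN (ULN 1.1), so not only at the ceiling. The next two depend on the ULN. The last is never below 30.

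**Step 3: how light must a subject be?** Setting CrCl = 30 at the ceiling gives weight = 30 × 72 × ceiling ÷ [(140 − age) × (0.85 if female)]. For a woman of 75: 2160 × 1.35 ÷ 55.25 = 52.8 kg, and 2160 × 1.65 ÷ 55.25 = 64.5 kg.

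| Age | Women, kg (low to high ULN) | Men, kg (low to high ULN) |
|---|---|---|
| 70 | 49.0 to 59.9 | 46.3 to 60.2 |
| 75 | 52.8 to 64.5 | 49.8 to 64.8 |
| 80 | 57.2 to 69.9 | 54.0 to 70.2 |

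Below these weights a subject at the creatinine ceiling has CrCl under 30 and still satisfies the renal row of Table 5.

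**The case against.** **The advice is background.** It sits in a literature summary, cautiously worded, and rests on 4 patients. This stands: it is advice not carried forward, not a clash between two operative rules.

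**The evidence is thin and from a higher dose.** The 4 patients received 1250 mg/m², whereas Section 4.6.1 chooses 1000 mg/m² for tolerability. Section 4.5.1 gives no rate for the other 20 patients, and the exact 95% lower limit for 4 of 4 is 0.025^(1/4) = 0.40. A reader might infer that severe toxicity at the trial's dose is established; the documents do not show that. Still, the reported advice is avoidance, not a lower dose.

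**Other checks apply before dosing.** The tumor board includes pharmacology expertise and lists patient safety among its criteria (Section 4.1). A physician signs the eligibility checklist (Section 6.1). Section 5.2 allows exclusion on judgement, and Section 9.4.7 requires laboratory results to be found acceptable before each dose. These lower the risk. None states a threshold or requires a clearance, and a creatinine within Table 5 would look acceptable.

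**The limit may exist elsewhere.** A reader might infer that the trial has no renal rule at all. The documents do not support that: the agent subprotocol and package insert are not supplied, and the footnote to calculated clearance in Table 5 is not visible. Package-insert alignment cannot simply be presumed to fill the gap, however, because the 1000 mg/m² start already departs from the approved 1250 mg/m².

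**The examples are chosen.** They are elderly and light, with creatinine at or near the ceiling. This stands too: they show that the gap is possible, not how often it occurs.

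**Conclusion.** The point holds in a limited form. As far as the supplied text shows, a subject with CrCl below 30 mL/min can meet Table 5, pass Section 5.2.1 and start capecitabine at 1000 mg/m² twice daily, although Section 4.5.1 reports advice to avoid the drug in that subject. The textual gap needs no calculation; the illustration rests on Cockcroft-Gault and on assumed ULN, age and weight.

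The size is small. The plan expects a minimum of 9 treated subjects (Section 12) and estimates 15 entering Part 2 (synopsis), across all drugs. ECOG 0 or 1 is required, and the albumin and weight-loss criteria also apply. Frequency cannot be estimated from the documents. The consequence is for individual safety only.

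A reader might also infer a dosing error at CrCl 30 to 50 mL/min, where Section 4.5.1 mentions 75% of the recommended starting dose. The documents do not support this, because that sentence does not settle which starting dose is meant: 75% of the approved 1250 is 937.5 mg/m², while 75% of the trial's own 1000 is 750 mg/m². No error follows from an unsettled reference dose.

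**What to change.** 1. For each capecitabine candidate, calculate and record CrCl at screening by a named formula, from age, weight and the metabolic panel already collected under Table 7.
2. Add CrCl below 30 mL/min to the exclusions in Section 5.2.1. If the capecitabine subprotocol already holds this limit, a cross-reference from Section 5.2.1 is enough.

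Table 5 can stay as it is for the other agents. The cost is one calculated field and one line of text, with no new test. The downside is that a rare subject loses capecitabine as an option and would need another matched drug.
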